3. STUDY DESIGN

This is a single-center, randomized, open-label (unblinded), parallel-group controlled clinical trial evaluating the efficacy of a sequential multimodal intervention (structured physical exercise followed by SHP-based intergenerational activities) compared to nutritional education alone in community-dwelling elderly aged 60–75 years with physio-cognitive decline syndrome (PCDS).

The study duration per participant is 16 weeks, consisting of:

- Baseline assessment (week 0)
- Intervention period: 12 weeks of chair-exercise + 4 weeks of intergenerational activities (intervention arm) or continued education (control arm)
- Intermediate assessment (end of week 12)
- Final assessment (end of week 16)

Participants are randomized in a 1:1 ratio into two arms:

- Intervention arm (n=50): Nutritional education + 12 weeks structured chair-based exercise (PEROSI protocol, progressive frequency from 1 to 3 sessions/week, 60 minutes/session, supervised online) followed sequentially by 4 weeks SHP-based intergenerational activities (8 sessions, 2x/week, 45 minutes/session, paired 1:1 elderly-child using AMIR educational materials at selected orphanages).
- Control arm (n=50): Nutritional education only (2 personalized dietitian tele-conferences at weeks 1 and 11; 5 educational e-flyers at weeks 3, 5, 7, 13, and 15).

Randomization is computer-generated using permuted block randomization (block size 4), stratified if necessary, with allocation concealment managed by an independent third party. Blinding of participants and instructors is not feasible due to the nature of the behavioral interventions; however, outcome assessors for laboratory analyses (mBDNF) are blinded to group allocation where possible.

The trial follows intention-to-treat principles with per-protocol sensitivity analysis. Recruitment targets consecutive eligible elderly from community programs under the School of Medicine and Health Sciences at Atma Jaya Catholic University of Indonesia and the Archdiocese of Jakarta. Child participants (aged 5–8 years, n=50) are recruited from cooperating orphanages exclusively for the intervention arm.

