7.3.8 Monitoring and adherence

Adherence and safety are monitored proactively to maximize retention and minimize risks.

- Adherence monitoring:
 - Exercise sessions (intervention arm): Attendance logged by instructor and research assistant; session completion confirmed ($\geq 85\%$ of planned sessions required for per-protocol analysis).
 - Intergenerational activities: Attendance sheets signed by research team and orphanage staff; activity completion checklists.
 - Nutritional education (both arms): Confirmation of tele-conference attendance and e-flyer receipt/viewing (via read receipts or follow-up query).
 - Overall: Monthly telephone counseling (2–3 calls/month) by research team to encourage compliance, address barriers, and reinforce motivation.
- Safety monitoring:
 - During exercise phase: Weekly (Monday) pre-session symptom and condition checks by team/instructor; Borg Rating of Perceived Exertion scale monitored throughout sessions; immediate termination for excessive symptoms (severe dyspnea, palpitations, dizziness, heavy weakness, pre-syncope).
 - Bi-weekly direct evaluations (weeks 4, 6, 8, 10): Remote or in-person query on complaints, with direct supervision during selected sessions.
 - Intergenerational phase: On-site supervision by research team and orphanage staff; post-session brief feedback on comfort/discomfort.
 - General: Participants provided with contact number for immediate reporting; all potential adverse events (fatigue, muscle pain, emotional discomfort, minor injuries) documented, managed, and reported to Ethics Committee if serious.

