7.5 Withdrawal of individual subjects

Participants (elderly or children via orphanage representative) may withdraw voluntarily at any time without providing reasons and without impact on routine care or relationship with researchers. Withdrawal is documented but no further study procedures performed unless consented for final assessment.

Investigator-initiated withdrawal occurs for:

- Development of exclusion criteria (e.g., new disability, dementia suspicion, uncontrolled chronic disease).
- Acute illness requiring hospitalization or prohibiting continuation (e.g., pneumonia, acute stroke, uncontrolled hypertension).
- Non-adherence (>3 consecutive missed exercise sessions or <85% overall intervention completion).
- Intolerable adverse events suspected related to intervention.

Withdrawn participants are encouraged to complete safety follow-up and/or final assessments for intention-to-treat analysis. All withdrawals are fully documented (reason, date, partial data

collected) and reported to Ethics Committee if related to safety. No replacement of withdrawn subjects.

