7.5.1 Drop out Criteria

Subjects are classified as drop-outs if they do not complete the study protocol through the final assessment (week 16) for any reason. Specific drop-out criteria include:

- Non-adherence to intervention: Failure to attend >3 consecutive structured exercise sessions (intervention arm) or $<85\%$ of total planned exercise sessions; failure to attend ≥ 2 intergenerational activity sessions or $<85\%$ overall attendance for SHP phase.
- Development of exclusion criteria during study: New onset of disability, suspected/confirmed dementia, depression (GDS-15 score indicating moderate-severe depression requiring intervention), total immobility, uncontrolled chronic disease, or hemodynamic instability.
- Acute illness or clinical worsening: Occurrence of acute conditions (e.g., pneumonia, acute arthritis with VAS $>6/10$, acute stroke, acute myocardial infarction, uncontrolled hypertension $\geq 180/100$ mmHg, acute COPD exacerbation) requiring hospitalization or prohibiting continuation.
- Adverse events suspected related to intervention: Intolerable or serious symptoms (e.g., persistent severe fatigue, muscle pain, dizziness, fall during exercise, significant emotional distress during intergenerational activities) leading to investigator decision for withdrawal.
- Voluntary withdrawal: Subject (or orphanage representative for children) requests discontinuation for any personal reason (e.g., lack of time, loss of motivation, transportation difficulties).
- Loss to follow-up: Inability to contact subject despite ≥ 3 attempts via phone/WhatsApp over 2 weeks, or permanent relocation outside study area.
- Death: Any mortality during study period (reported immediately as serious adverse event).

All drop-outs are documented in detail (date, reason, last completed assessment/procedure) on the case report form and in the trial master file.

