7.6 Replacement of individual subjects after drop out

Dropped-out subjects are not replaced. The initial sample size calculation (minimum 100 elderly participants, 50 per group) incorporates an anticipated drop-out rate of up to 15% (based on similar community-based geriatric intervention studies) to ensure sufficient statistical power for primary endpoints. Child participants are paired 1:1 with elderly in the intervention group; if an elderly participant drops out during the SHP phase, the paired child continues if feasible and

willing, or the session is adjusted accordingly without recruitment of new children. No over-recruitment or replacement strategy is employed to maintain the integrity of consecutive recruitment and randomization.

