9. STATISTICAL ANALYSIS

All collected data will be initially recorded on research case report forms (CRFs) and subsequently transferred to secure electronic storage for data cleaning, coding, and verification. Descriptive data and analytical results will be presented in narrative text, tables, or figures as appropriate.

Normality of data distribution will be assessed using the Kolmogorov-Smirnov or Shapiro-Wilk test ($p > 0.05$ indicates normal distribution). Normally distributed continuous data will be presented as mean \pm standard deviation (SD); non-normally distributed data as median with minimum-maximum range. Categorical data will be presented as frequencies and percentages. Statistical significance will be set at $p < 0.05$. All analyses will be performed using SPSS version 20 software.

Primary analyses will be conducted on the per-protocol (PP) population, excluding drop-out subjects. Between-group comparisons of changes in study outcomes (hand grip strength, gait speed, MoCA-Ina score, serum mBDNF levels, and health-related quality of life) will use unpaired t-tests (parametric) or Mann-Whitney U tests (non-parametric), selected based on normality test results.

Correlations between serum mBDNF levels and MoCA-Ina score, hand grip strength, and gait speed will be evaluated using Pearson correlation (for normally distributed variables) or Spearman correlation (for non-normally distributed variables), according to normality assessment of each variable.

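### Section 9 makes per-protocol the primary analysis, against the intention-to-treat principle in Section 3, and the attendance rules then remove poor attenders from the intervention arm only

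*Combined protocol and SAP*

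**What the plan says.** Two sections name different primary analysis sets.

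- Section 3 (Study design): "The trial follows intention-to-treat principles with per-protocol sensitivity analysis".
- Section 9 (Statistical analysis): "Primary analyses will be conducted on the per-protocol (PP) population, excluding drop-out subjects". Section 9 describes no intention-to-treat analysis.

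Three sections decide who leaves the per-protocol set or the study because of attendance.

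- Section 7.3.8, under exercise sessions in the intervention arm, sets 85% "of planned sessions required for per-protocol analysis".
- Section 7.5.1 classes a participant as a drop-out for "Failure to attend >3 consecutive structured exercise sessions (intervention arm") or for under 85% of planned exercise sessions. It does the same for "failure to attend ≥ 2 intergenerational activity sessions" or under 85% attendance in the SHP phase.
- Section 7.5 lists as a reason for investigator-initiated withdrawal: "Non-adherence (>3 consecutive missed exercise sessions or <85% overall intervention completion"). It then says: "Withdrawn participants are encouraged to complete safety follow-up and/or final assessments for intention-to-treat analysis". Section 7.7 repeats that encouragement.

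Section 5.1 states that controls take part in neither the exercise nor the SHP sessions. Section 7.3.8 confirms contact with nutritional education in both arms but attaches no threshold to it. Section 7.6 says the sample size "incorporates an anticipated drop-out rate of up to 15" per cent.

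**The concern.** Sections 3 and 9 cannot both be followed. If both stand, the analysis population could be settled after the results are known.

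If Section 9 governs, the primary set is whoever survives Section 7.5.1, the strictest of the three rules. Its attendance criteria act in one arm only. Older adults who attend nearly every session may be healthier or more motivated, and may change differently for those reasons alone. Removing poor attenders from one arm lets that difference into the estimated effect. Section 7.2 describes the trial as open-label, with only the mBDNF laboratory analysts blinded, so little else in the design would offset it.

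The second risk is lost data. Section 7.5 withdraws non-adherent participants and only encourages a week-16 assessment. Values not collected cannot be recovered later, even if the analysis text is corrected.

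**Working it through.** **The plan's own figure.** Section 4.5 gives a largest requirement of 42 per group, and Section 7.6 allows 15% drop-out. 42 / (1 − 0.15) = 49.4, rounded up to 50 per group, which reproduces the plan. The allowance is 0.15 × 50 = 7.5 people per arm.

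**Session counts (Section 5.1).** Exercise: 2×1 + 4×2 + 6×3 = 28. SHP: 8. Total: 36.

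**What Section 7.5.1 requires.**
- Exercise: 0.85 × 28 = 23.8, so at least 24 of 28, with no run of four misses.
- SHP: 0.85 × 8 = 6.8, so at least 7 of 8. Two misses give 6/8 = 75% and exclusion.

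**How many are kept.** The documents give no attendance rates, so these are assumed. For independent sessions at 90% attendance, ignoring the run-of-misses rule, P(at least 24 of 28) = 0.858 and P(at least 7 of 8) = 0.813. The product is 0.698, or about 35 of 50. The table adds the run rule and a version in which attendance clusters within people (beta-binomial, correlation 0.3), simulated with 400,000 people per setting.

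| Mean attendance | Kept of 50, independent | Kept of 50, correlation 0.3 |
|---|---|---|
| 85% | 19 | 31 |
| 90% | 35 | 37 |
| 93% | 43 | 41 |
| 95% | 47 | 44 |

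The attendance criteria remove none of the 50 controls. On their own they exceed the 7.5-person allowance below about 93% attendance (independent) or 94% (correlation 0.3). At 95% they do not: losses are 3.4 and 6.4.

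**Bias with no true effect.** Let r be the correlation between a person's attendance and the change score. The shift in the intervention mean is r times the average standardised attendance of those kept. With within-person correlation 0.3, that average is about 0.46 at 90% attendance and 0.31 at 95%. Error rates come from 20,000 simulated null trials per setting, comparing the kept intervention participants with 50 controls by t-test.

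| r | 90%: shift (SD) | 90%: two-sided error | 95%: shift (SD) | 95%: two-sided error |
|---|---|---|---|---|
| 0.1 | 0.05 | 5.5% | 0.03 | 5.0% |
| 0.2 | 0.09 | 6.8% | 0.06 | 5.9% |
| 0.3 | 0.14 | 9.7% | 0.10 | 7.4% |

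**Power.** Section 4.5 gives no effect size or SD. With a t-test, 80% power at 42 per arm implies a standardised difference of 0.619. At that value power is 79% with 35 against 50, and 76% with 35 against 42.5. The loss is minor, so the main harm is bias.

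**Sections 7.5 and 7.5.1 compared.** A participant with 28/28 exercise and 6/8 SHP sessions has 34/36 = 94%. If all 36 sessions form the denominator in Section 7.5, that person is not withdrawn, yet is a drop-out under Section 7.5.1. Section 7.5 does not define its denominator. On the 36-session reading, the two rules differ at 90% attendance by 42.7 − 34.8, about 8 people (independent), or 39.0 − 37.3, about 2 people (correlation 0.3).

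**The case against.** The conflict between Sections 3 and 9 is not in dispute. The case on the other side concerns its size and its limits.

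- *Controls are selected too.* Illness, new exclusion criteria, voluntary withdrawal and loss to follow-up are drop-out reasons in both arms. This stands. The accurate statement is that controls are not selected on exercise or SHP attendance. The overall-completion rule in Section 7.5 might be stretched to nutritional education in controls, but no control threshold is defined.
- *The bias figures are conditional.* They need an attendance rate, a within-person correlation and an attendance–outcome correlation, and the documents supply none of these. Sections 5.2 and 7.3.8 plan two to three support calls a month, and Section 10.4 offers transport help, so attendance may be high. This stands as a limit on size, and is why the 95% results appear beside the 90% ones. The direction is also an assumption.
- *One primary endpoint is not covered.* Section 7.1.1 names frailty status and mBDNF. SD shifts do not describe a three-category frailty status. The power figures use the outcome that needed 42 per group, which Section 4.5 does not identify. Both points stand.
- *Sections 7.5 and 7.5.1 serve different purposes.* One governs withdrawal and the other drop-out classification, so different thresholds need not conflict. This is fair, and the gap is secondary.
- *Data loss is partly handled.* Sections 7.5 and 7.7 encourage final assessments, and Section 7.4 allows home visits. This reduces the risk without removing it, because nothing requires the assessment.

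None of these points reconciles the two sections or makes the attendance rules symmetric.

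**Conclusion.** The concern holds. The contradiction over the primary population, and the fact that the exercise and SHP criteria can exclude only intervention participants, follow from the text and need no assumption. How many are excluded and how far the estimate moves depend on the assumed attendance and correlations. Over the settings examined, the bias in a continuous outcome runs from small (0.03 SD, error essentially 5%) to material (0.14 SD, error about 10%). The effect on frailty status is not quantified. The plan should be changed, and before follow-up data are lost.

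**What to change.** - **Section 9:** make the primary analysis include every randomised participant in the assigned arm, whatever their attendance, as Section 3 already promises. State how missing week-16 values are handled. For continuous outcomes, a mixed model using weeks 0, 12 and 16 is one option.
- **Sections 7.5 and 7.5.1:** stop treating non-adherence as study withdrawal or drop-out. Low attenders at most stop the intervention and are still assessed at week 16.
- **Section 7.3.8:** give one attendance definition, with a stated denominator and separate exercise and SHP thresholds, used only for the per-protocol sensitivity set.

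The cost is wording in four sections. Week 16 is already scheduled for everyone, so no visit is added.

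The statistical price is dilution. With 50 per arm and the implied difference of 0.619, power is 86%. If 15% of the intervention arm gain nothing (assumed), the difference falls to 0.619 × 0.85 = 0.53 and power to about 74%. If 30% gain nothing, it falls to 0.619 × 0.70 = 0.43 and power to about 57%. The 15% allowance covers lost numbers and not this dilution, so the sponsor should accept the lower power knowingly or revisit the sample size.

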Intervention: Both groups receive nutritional education. Participants in the intervention group will receive a structured chair-based exercise program followed by guided intergenerational activities designed to enhance physical capacity, cognitive stimulation, and social engagement. The control group will receive usual care. Intervention group: 12 weeks structured chair-exercise (PEROSI protocol, progressive frequency 1-3x/week, 60 min/session) followed by 4 weeks SHP (8 sessions, 2x/week, 45 min, paired elderly-child activities using AMIR materials). The control group will receive education only.

Main study parameters/endpoints: The primary outcomes include changes in physical performance and cognitive function. Secondary outcomes include changes in frailty status, quality of life, and psychosocial well-being.

Nature and extent of the burden and risks associated with participation, benefit, and group relatedness: Participation in this study involves minimal to low risk. The primary potential risks are related to the structured chair-based exercise, including mild musculoskeletal discomfort, transient fatigue, muscle soreness, dizziness, or shortness of breath, particularly during the initial sessions. These risks are considered low and are commonly associated with light-to-moderate physical activity in older adults. To minimize these risks, all exercise sessions will be conducted under supervision by trained personnel, with prior health screening and continuous monitoring of participants' physical condition.

Intergenerational activities are non-invasive and pose no physical risk; however, minor psychological discomfort, such as temporary feelings of anxiety or social unease, may occur during initial interactions. These activities will be conducted in a supportive and controlled environment to ensure participants' comfort and emotional safety.

The overall burden to participants includes time commitment for attending intervention sessions and undergoing physical, cognitive, and laboratory assessments. Blood sampling for laboratory analysis may cause mild pain, bruising, or discomfort at the puncture site, with no expected long-term adverse effects.

Potential benefits for participants include improvement in physical function, cognitive performance, frailty status, social engagement, and overall quality of life. The anticipated benefits are considered to outweigh the minimal risks associated with study participation.

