4.5 Sample size calculation

The sample size was calculated to detect clinically meaningful differences between the intervention and control groups in key outcome measures, including handgrip strength, gait speed, cognitive function (MoCA-Ina score), health-related quality of life (SF-12), and serum mature brain-derived neurotrophic factor (mBDNF) levels.

Sample size estimation was performed using the formula for comparison of two independent means, with a two-sided significance level (α) of 5% and a statistical power ($1-\beta$) of 80%. The standard deviation and expected mean differences for each outcome were derived from previously published studies involving older adults, as no prior studies have specifically evaluated SHP-based interventions or their combination with structured physical exercise.

Based on these calculations, the required sample sizes for individual outcome parameters ranged from 9 to 42 participants per group. Considering the largest estimated sample size requirement and allowing for potential dropouts, the minimum required sample size for this randomized controlled trial was determined to be 100 older adult participants, with **50 participants allocated to each group (intervention and control)**.

This sample size is considered sufficient to evaluate the primary and secondary outcomes of the study and to ensure adequate statistical power while accounting for potential attrition during the study period.

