7. METHODS

7.1 Study parameters/endpoints

7.1.1 Main study parameter/endpoint

- Change in frailty syndrome status (assessed using Cardiovascular Health Study criteria: score 0 robust, 1–2 pre-frail, ≥3 frail) from baseline to week 16.
- Change in serum mature brain-derived neurotrophic factor (mBDNF) levels (measured by ELISA) from baseline to week 16.

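### Frailty is a primary endpoint in sections 2 and 7.1.1 but secondary in the Summary, and it has no between-group test in section 9 and no input to the sample size in section 4.5

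*Combined protocol and SAP*

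**What the plan says.** **Role of frailty.** The primary objective in section 2 names frailty syndrome and serum mBDNF. The hypothesis there leads with the same two, and claims a significantly better frailty status in the intervention arm. Section 7.1.1 lists as its first main endpoint "Change in frailty syndrome status (assessed using Cardiovascular Health Study criteria", in three ordered levels (robust, pre-frail, frail), from baseline to week 16; mBDNF is the second. The Summary differs: "The primary outcomes include changes in physical performance and cognitive function", and "Secondary outcomes include changes in frailty status, quality of life, and psychosocial well-being". Neither Summary list names mBDNF.

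**Analysis.** Section 9 specifies t-tests or Mann-Whitney U tests for "Between-group comparisons of changes in study outcomes (hand grip strength, gait speed, MoCA-Ina score, serum mBDNF levels, and health-related quality of life", and the list closes there. For categories it says: "Categorical data will be presented as frequencies and percentages". Its correlation paragraph does not mention frailty either.

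**Sample size.** Section 4.5 names its outcomes as "including handgrip strength, gait speed, cognitive function (MoCA-Ina score), health-related quality of life (SF-12), and serum mature brain-derived neurotrophic factor (mBDNF) levels". It uses the formula for two independent means (two-sided 5%, 80% power) and reports requirements of 9 to 42 per group. It then calls 50 per group sufficient for the primary and secondary outcomes. Section 7.6 says the size allows for up to 15% drop-out and protects power for the primary endpoints.

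**The concern.** The hypothesis makes a significance claim about frailty, and the analysis section provides no test that could support or refute it. An analyst would have to choose the measure (CHS score change, category shift or proportion improved) and the test with the data in hand.

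The two lists of primary outcomes have no endpoint in common as named, so a reader cannot tell which results the trial is to be judged on. The statements that the sample is large enough for the primary endpoints also cannot be traced to any frailty assumption.

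**Working it through.** **1. The passages side by side**

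| Place | Frailty | mBDNF | Grip, gait, MoCA-Ina |
|---|---|---|---|
| Section 2 | primary | primary | secondary |
| Section 7.1.1 and 7.1.2 | primary | primary | secondary |
| Summary | secondary | not listed | primary (as physical performance and cognition) |
| Section 4.5 | not shown | sized | sized |
| Section 9 | no test | tested | tested |

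Quality of life is secondary throughout, sized in 4.5 and tested in 9. The five outcomes sized in 4.5 are the five tested in 9, and frailty is missing from both.

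**2. The plan's own figure**

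Largest requirement 42, drop-out 15%: 42 / (1 − 0.15) = 49.4, rounded up to 50 per group. The stated size reproduces. Inverting the two-means formula, d = (1.960 + 0.842) × √(2/n), gives d of about 0.61 for n = 42 and 1.32 for n = 9. These are standardised mean differences for continuous outcomes and carry no information about a three-level category.

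**3. What 42 evaluable per arm could show for frailty**

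No frailty distribution or effect is given, so the control splits (robust/pre-frail/frail) below are assumptions. Whitehead's formula for an ordinal comparison, N = 84 in total, two-sided 5%, no baseline adjustment:

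power = Φ( |ln OR| × √( N × (1 − Σp̄³) / 12 ) − 1.96 ), where p̄ is the mean of the two arms' proportions in each category.

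Worked case, control 20/60/20 and OR = 2: the intervention arm becomes 33.3/55.6/11.1, so p̄ = 0.267, 0.578, 0.156 and Σp̄³ = 0.216. Then √(84 × 0.784 / 12) = 2.343, and 0.693 × 2.343 − 1.96 = −0.336, so power is 37%.

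| Assumed control split | OR for 80% power, 42 per arm | Power at OR 2, 42 per arm | OR for 80% power, 50 per arm | Power at OR 2, 50 per arm |
|---|---|---|---|---|
| 10/80/10 | 3.94 | 26% | 3.6 | 30% |
| 10/70/20 | 3.60 | 31% | 3.3 | 36% |
| 20/60/20 | 3.25 | 37% | 3.0 | 43% |
| 20/50/30 | 3.14 | 39% | 2.9 | 45% |

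At 20/60/20 with 42 per arm, an odds ratio of 3.25 means moving the intervention arm to about 45/48/7. A more concentrated split of 2/90/8 would need about 6.7. A simulation check (500 runs each, unadjusted proportional-odds model, 42 per arm) gave 31% at 10/70/20 and 39% at 20/60/20 for an odds ratio of 2. For an odds ratio of 3 it gave 62% and 71%, against 66% and 74% by formula, so the formula is slightly optimistic at larger effects.

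**4. An assumed dichotomy, for illustration**

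Endpoint: improved by at least one category. With 42 per arm and a pooled null variance, 80% power needs 27.1% vs 5%, 35.2% vs 10%, 48.6% vs 20% or 60.0% vs 30%. These are differences of about 22, 25, 29 and 30 points. Power for 40% vs 20% is 52%.

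**5. Contrast with mBDNF**

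If mBDNF's own 80% requirement was 9, 20, 30 or 42 per group, 42 per arm gives power of over 99%, 98%, 91% or 80%. The power claim is therefore supported for one primary endpoint and not for the other.

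**6. Two primaries at 5% each**

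If either alone counted as success, the family-wise error would be 1 − 0.95² = 9.75% under independence. If both are required, no adjustment is needed.

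**The case against.** The strongest reply is that this is a drafting slip. Section 9 already names Mann-Whitney U, which suits an ordinal change, so adding frailty to the list would close most of the gap. That is a reasonable repair, but the text ties the test to the five listed outcomes, selects it by a normality test and does not define the frailty measure.

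It can also be said that the Summary's list may be the intended one, because those outcomes are both sized and tested. Against this, the closing aim of section 1, the objective, the hypothesis and section 7.1.1 all agree with one another, and the Summary stands alone.

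Three smaller points carry some weight:
- Section 4.5 introduces its outcomes as examples, so strictly one can say only that no frailty input is shown. The two-means formula makes a hidden one unlikely.
- The hypothesis joins the two primaries with a conjunction, which suggests both are needed. Multiplicity is then a matter for clarification.
- The power figures depend on the assumed split, ignore baseline adjustment and improve somewhat with 50 per arm. They show a range, and the defect does not rest on them.

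Testing grip and gait is not a substitute: they supply two of the five CHS criteria in section 7.3.4.

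**Conclusion.** The concern holds and should be resolved before any outcome data are analysed. That frailty's status conflicts, that no test is named and that no sizing input is shown all follow from the text alone, with no assumption. The numerical size rests on assumed control splits, complete data on 42 per arm and an unadjusted analysis. On that basis the trial is likely to detect only large shifts in frailty and would usually miss an odds ratio of 2. How far baseline adjustment would change this cannot be computed from the documents. The arithmetic behind 50 per group is sound for the outcomes it covers.

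**What to change.** 1. **Summary:** name frailty status and mBDNF as primary, in line with sections 2 and 7.1.1.
2. **Section 9:** add frailty with a pre-specified ordinal between-group analysis. One option is a proportional-odds model of week-16 CHS category on arm and baseline CHS score, reporting the common odds ratio with its 95% confidence interval. The population is whichever the sponsor fixes when it reconciles section 3 ("The trial follows intention-to-treat principles with per-protocol sensitivity analysis") with section 9 ("Primary analyses will be conducted on the per-protocol (PP) population, excluding drop-out subjects"). That conflict is a separate matter.
3. **Success rule:** state before analysis whether both primaries must succeed (no alpha adjustment, as the hypothesis wording suggests) or either one (adjust alpha).
4. **Sections 4.5 and 7.6:** limit the sufficiency claim to the outcomes actually calculated, and state what frailty effect about 42 evaluable per arm can detect, with the assumed distribution.

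The cost is wording in four places and one further analysis. The stated power will look less favourable. If the reconciled population is all randomised participants, a rule for missing week-16 CHS data is also needed. No visits or participants are added, because section 7.4 already schedules CHS at baseline, week 12 and week 16.
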